This study will be conducted in compliance with the protocol, Good Clinical Practice and the applicable Food and Drug Administration and other Department of Health and Human Services regulatory requirements.

All key personnel (all individuals responsible for the design and conduct of this study) have completed Human Subjects Protection and Good Clinical Practice training.

IV. IRB Oversight

Human Subjects Office / IRB

J. [name]

[name]

[name]

[name]

FWA#: FWA00003007

Voice: [contact]

[contact]

Email: [contact]

V. Location of Study Procedures

University of Iowa
[name]
[name]

VI. Main Hypothesis

HHHFA during sleep in COPD patients with chronic bronchitis improves respiratory symptoms, sleep quality, lung function, and exercise capacity.

VII. Main Screening Criteria

We will recruit COPD men and non-pregnant women of any ethnic background with the age above 18 years with the following characteristics: post-bronchodilator FEV1%predicted below 70%, chronic bronchitis defined as cough with daily sputum production, and at least 1 exacerbations in the last year.

VIII. Recruitment procedures

The study team will utilize email blasts and University of Iowa Noon News advertising to recruit subjects for this study. We will also advertise study at the Iowa City VAMC. Upon study beginning and ensuring the smooth operation of the protocol, we will apply to the VA for permission to recruit subjects from the Iowa City VAMC. To avoid any coercion all subjects are offered the opportunity to talk with their primary care provider or family prior to signing a consent form. Study participation has no influence on their medical care.

IX. Inclusion Criteria

- COPD diagnosis by health care provider
- Smoking with at least 10 pack-years
- Post-bronchodilator FEV1/FVC <0.7
- Post-bronchodilator FEV1%predicted <70%
- Chronic bronchitis, defined as chronic cough with daily sputum production
- ≥1 COPD exacerbations within the last year

X. Exclusion Criteria

- Obstructive sleep apnea or suspected obstructive sleep apnea that requires positive airway pressure treatment
- Patients that use oxygen supplementation continuously (patients that use oxygen supplementation only at exertion, as needed, or at night will NOT be excluded)
- Any planned procedure that makes ineligible according the PI clinical judgement
- Unable to perform a spirometry, 6-minute walk test or chest CT

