Baseline visit. After randomization, participants will have baseline measurements and training in the device. Participants will provide information regarding demographics, medical history, COPD history including prior exacerbations, hospitalizations, and pertinent medication use. Weight, height, and vitals will be recorded. Participants will complete Medical Research Council dyspnea scale (MRC),[45] St. George's Respiratory Questionnaire (SGRQ),[46-48] COPD Assessment Test (CAT),[49], Pittsburgh Sleep Quality Index (PSQI),[50], and Cough and Sputum Assessment Questionnaire (CASA-Q).[51] Subsequently, participants will perform a 6-minute walk test follow by an inspiratory and expiratory chest CT. Chest CT will be performed based on quantitative CT lung protocols.[52] TLC and residual volume (RV) will be measured at maximal inspiration and maximal expiration, respectively. We will quantify % emphysema and % gas trapping based on chest CT images. Quantified % emphysema will be defined as the percentage of voxels less than -950 Hounsfield units at TLC. Quantified % gas trapping will be measured at TLC as the percentage of voxels less than -856 Hounsfield units at RV. A parametric response map (PRM) will be constructed to reduce the misclassification of emphysema as gas trapping. Voxels with emphysema on TLC will be eliminated from the voxel count of gas-trapped areas after image matching of TLC and RV images. Airway geometry including Pi10, wall thickness, and visual mucus plugs will also be assessed.[52, 53] Lastly, subjects will receive training and the HHHFA with information materials and a study personnel contact number.

Phone Call at Week 1. Three to seven days after enrollment, a member of the research team will contact the participant to address any concerns or questions regarding the device (device training) and/or the study, and adverse events.

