Follow-up visit (6-weeks). After 6 weeks, participants will return to the CRU with the HHHFA device and perform the same procedures in the same order as at the baseline visit including weight, height, vitals, spirometry, MRC questionnaire, CAT questionnaire, PSQI questionnaire, CASA-Q questionnaire, 6-min walk test, inspiratory and expiratory chest CT. Information regarding changes in medication usage including frequency of rescue inhaler, exacerbation and hospitalizations since the last visit will also be collected. Participants in the HHHFA arm will be asked whether they want to continue to participate in the sub-study that will have them use the HHHFA for an additional 42 weeks. Participants that are not interested in participating in the sub-study, will return the device at the 6 week follow-up visit. Participants interested in participating in the sub-study can ship the device to the research team following their completion of the sub-study that will end at 48-weeks.

Phone Call visit at 12-weeks Only participants in the HHHFA sub-study group will receive a phone call at 12 weeks. Assessment for respiratory exacerbations will be performed.

Protocol: Heated, humidified high-flow air in Chronic Bronchitis

October 8, 2020

HHHFA V4.0

Phone Call visit at 24-weeks. Only participants in the HHHFA sub-study group will receive a phone call at 24 weeks. Assessment for respiratory exacerbations will be performed.

Phone Call visit at 36-weeks. Only participants in the HHHFA sub-study group will receive a phone call at 36 weeks. Assessment for respiratory exacerbations will be performed.

Phone Call visit at 48-weeks. Only participants in the HHHFA sub-study group will receive a phone call at 48 weeks. Assessment for respiratory exacerbations will be performed. Patients will ship the HHHFA device back to the company.

Table 1. Schedule of events summary

[figure not shown]
Activity	Visit 1	Phone Call visit (week 1)	Follow-up visit (6-weeks)	Phone Call visit (12-weeks)	Phone Call visit (24-weeks)	Phone Call visit (36-weeks)	Phone Call visit (48-weeks)
Informed Consent	X						
Screening evaluation and enrollment	X						
Spirometry	X		X				
Demographics and medical history	X		X				
Respiratory condition-related medications only	X		X				
Modified physical exam	X		X				
SaO ₂ at rest	X		X				
Randomization	X						
HHHFA device training and support	X	X	X	X	X	X	X
MRC questionnaire	X		X				
SGRQ Questionnaire	X		X				
CAT score	X		X				
PSQI	X		X				
CASA-Q	X		X				

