6-MWT	X		X				
Chest CT	X		X				
Respiratory exacerbation assessment	X	X	X	X	X	X	X
Adverse events	X	X	X	X	X	X	X
HHHFA Return device			X	X	X	X	X

Protocol: Heated, humidified high-flow air in Chronic Bronchitis

October 8, 2020

HHHFA V4.0

Protocol Summary

XII. Study procedures

Vitals, Height and Weight

The subject will have vitals taken by a CRU nurse: Height, weight, blood pressure, SaO₂ (saturation of oxygen in the blood), heart rate, temperature, and breathing rate. This will take approximately 20 minutes.

Six-min walk test

The test measures the distance a patient can walk on a flat, hard surface in six minutes.

Urine Pregnancy Test

Women of childbearing potential will have a urine pregnancy test as well. Before beginning the CT and MRI scans, the urine pregnancy test for females of childbearing potential will be checked. If the result is positive for pregnancy subject will be withdrawn.

Spirometry

The subject's FEV₁, FVC and the FEV₁/FVC ratio will be determined after three acceptable spirometry efforts are obtained. After prebronchodilator spirometric manoeuvres, two puffs of albuterol metered dose inhaler were administered using a spacer. Postbronchodilator manoeuvres were performed between 15 and 20 min.

CT Scans

The subject will be then taken to the Research CT Imaging Suite for their CT scan. A CT scan combines a series of X-ray images taken from different angles and uses computer processing to create cross-sectional images of the lungs. The CT scan will provide more detailed information than a standard x-ray. Once in the CT lab, the subject will be asked to remove any metallic items from their person (jewelry, piercings that can be removed easily, etc.). If the items to be removed involve clothing, the subject will be allowed to change in a

private restroom within the CT Suite and will be given a hospital scrub top to wear. We will explain the scanning procedures again to the subject and they will be reminded that they may ask questions at any time during the procedure(s). The subject will then be placed on the movable exam table of the CT scanner.

Three scans will be done in the CT scanner. One scout scan will be done to position the subject and then a total of two non-contrast CT scans will be done: Total Lung Capacity (TLC) and Residual Volume (RV).

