The first scan that will be done is called a scout scan. This brief scan, which is similar to an x-ray, is simply used to help the technologists make sure that the subject is positioned correctly. The subject will then be told to take in as deep of a breath as they can and hold it while the scout scan is done.

Total Lung Capacity (TLC) the subject will be asked to take a deep breath and blow out completely two times, they will then be asked to take a deep breath and hold their breath while the CT scan is being done. This breath hold will last approximately 5-8 seconds.

Residual Volume (RV). For this scan, we will tell the subject to take in a deep breath and blow it out twice before instructing them to take another deep breath in and blowing all of their air out until we see they've reached 0-10% of their SVC and then we will tell them to hold their breath while an image is being taken at RV (5-10 seconds).

Subjects will be asked to bring their cigarettes or electronic cigarettes with them to the visit. They will be asked to smoke one of their cigarettes or vape with their electronic cigarette. They will then repeat the same CT scans.

The spiral volumetric scan protocols use dose modulation with 36 reference mAs, 120kV, pitch of 1, & rotation time of 0.5sec. The CTDIvol for one scan at 36mAs is 2.41mGy, with total DLP of 81.5mGy cm for a 30cm scan.

Total effective dose equivalents (HE) for one spiral volumetric scan is estimated to be 160mrem

Total effective dose equivalents (HE) for TLC and RV spiral volumetric scan combined is estimates to be 320mrem

320mrem is ~8% of annual radiation limit for a medical worker.

Total mrem is 640 or ~16% of annual radiation limit for a medical worker.

Heated humidified high flow air (HHHFA)

Participants will be provided the HHHFA at baseline visit (time 0). At follow-up visit (6 weeks), participants using the HHHFA that are not interested in participating in the sub-study, they can return the device at the follow-up visit (6 weeks) . Participants that will participate the sub-study they can ship the device back to the research team at the end of the sub-study(48 weeks).

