Participants will be instructed to use the HHHFA for at least 4 hours during their sleep but will be allowed to use it as long as they want during sleep.[43] HHHFA will be administered using myAIRVO 2 device (Fisher & Paykel Healthcare), which provided humidified high-flow gas via Optiflow nasal cannula interface (Fisher & Paykel Healthcare). The temperature will be set at 32-37°C and flow will be set at 35L/minute but can be titrated down to 20L/minute for comfort based on a previous study.[44] Subjects use oxygen at night can blend the oxygen at the same flow through the device. Adherence of the device will be recorded using the device log.

XIII. Possible Risks of the Study

Spirometry: The subject may become short of breath or experience chest tightness while doing the pulmonary function tests.

CT scans: The subject will be exposed to radiation from the CT scans.

Heated humidified high flow air (HHHFA): According to a previous randomized control trials, that HHHFA applied during the night, six of 32 participants experienced adverse effects related to HHHFA.[43] Four participants experience night sweat, one had nasal discharge, one had insomnia, and one had a skin rash. Other adverse effects associated with the HHHFA device include but are not limited to the following: fire, burns, nosebleed, dry mouth and throat, headache, tripping over the equipment, electrical shock and injury, noise irritation, low oxygen due to improper use of device, skin irritation and injury/damage.

Possible Loss of Confidentiality: To reduce risk of a loss of confidentiality, precautions will be taken to ensure privacy. The PI and study team will maintain appropriate medical and research records for this study, in compliance with ICH E6 GCP, Section 4.9 and regulatory and institutional requirements for the protection of confidentiality of subjects. Research records generated in this study will be stored in file cabinets in a locked room and/or on a secure electronic database. The text message server stores the minimum amount of data possible-participant phone numbers and text message responses, no other participant information will be stored on that server. Only authorized study team at the sites will have access to the data. Imaging collected during the study will be identified by a subject number, IRB protocol number, and date of collection.

Abnormal findings:

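### The CT procedure asks participants to smoke or vape and then be rescanned, contradicting its own two-scan count, with no support elsewhere in the plan and no stated dose total that covers it

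*Protocol*

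**What the plan says.** The CT procedure in Protocol Section XII (V4.0, 8 October 2020) first sets out one session: a scout scan for positioning, and then "a total of two non-contrast CT scans will be done: Total Lung Capacity (TLC) and Residual Volume (RV"). After describing the breath-holds for these scans, it adds a separate three-sentence paragraph. That paragraph opens with "Subjects will be asked to bring their cigarettes or electronic cigarettes with them to the visit" and goes on: "They will be asked to smoke one of their cigarettes or vape with their electronic cigarette. They will then repeat the same CT scans". It is not marked optional, limited to current users or tied to a named visit.

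The dose lines follow directly. They give 160 mrem for one volumetric scan and 320 mrem for the TLC and RV pair, and end with "Total mrem is 640 or ~16% of annual radiation limit for a medical worker".

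The other parts of the plan that bear on this are:

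- **Section XI, baseline visit:** "participants will perform a 6-minute walk test follow by an inspiratory and expiratory chest CT".
- **Section XI, 6-week visit:** the baseline procedures are repeated in the same sequence, and the list ends with "6-min walk test, inspiratory and expiratory chest CT".
- **Table 1:** Chest CT is marked at Visit 1 and at 6 weeks, without a scan count. There is no row for smoking or vaping.
- **Section IX:** the only smoking criterion is "Smoking with at least 10 pack-years".
- **Section XIII:** "CT scans: The subject will be exposed to radiation from the CT scans". A separate list covers false-positive, incidental and missed findings. Neither mentions smoking or vaping.

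**The concern.** The paragraph describes an acute smoking or vaping challenge with imaging before and after. Nothing else in the plan describes such an experiment. Aim 2 uses CT to ask whether HHHFA during sleep changes air trapping and hyperinflation. Section XVIII contains no comparison before and after smoking, and the SAP covers only PSQI, CAT and the 6-minute walk.

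What is at stake is participant protection. Section IX admits patients with chronic bronchitis, post-bronchodilator FEV1 below 70% predicted and at least one exacerbation in the past year. Under the written procedure, staff would ask these patients to inhale smoke or vapour and then give them a second set of scans. The plan gives no purpose for this, lists no smoking or vaping risk, and states no study dose that includes the extra scans.

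Section III commits the study to being run in compliance with the protocol. Staff who follow the paragraph therefore expose patients without justification, and staff who skip it depart from the written procedure.

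**Working it through.** **Step 1. Scan counts.** The scout scan is left out because the protocol gives no dose for it.

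- Section XII before the paragraph: TLC + RV = 2 volumetric scans per session.
- Section XII with the paragraph: 2 + 2 = 4 per session.
- Section XI: one inspiratory and expiratory pair at each of two visits = 2 × 2 = 4 over the study.

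The conflict within Section XII is direct, since a stated total of two cannot also be four. The conflict with Section XI is by omission: that section lists the CT as one item per visit and mentions neither a smoking step nor a repeat.

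**Step 2. Reproduce the stated dose.** The input is 160 mrem per volumetric scan (Section XII).

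- One pair: 160 × 2 = 320 mrem, as stated.
- Two pairs: 320 × 2 = 640 mrem, as stated.
- Implied reference limit: 320 / 0.08 = 4,000 mrem and 640 / 0.16 = 4,000 mrem, so the two percentages agree.

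**Step 3. What 640 mrem can mean.** Two pairs arise in two ways:

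- one pair at each of two visits, with no repeat: 160 × 2 × 2 = 640 mrem;
- one visit with a pair before and a pair after smoking: 160 × 2 × 2 = 640 mrem.

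The dose line does not say whether it is per visit or per study, so 640 alone does not settle which was meant.

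**Step 4. Whole-study dose over both scheduled CT visits.**

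| Case | Volumetric scans | Dose (mrem) | Share of 4,000 mrem |
|---|---|---|---|
| No repeat | 4 | 4 × 160 = 640 | 16% |
| Repeat at one visit | 4 + 2 = 6 | 6 × 160 = 960 | 24% |
| Repeat at both visits | 4 + 4 = 8 | 8 × 160 = 1,280 | 32% |

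If 640 mrem is the study total, the repeat adds 960 − 640 = 320 mrem or 1,280 − 640 = 640 mrem that no figure covers. If 640 mrem describes one visit with a repeat, the repeat is counted but the other CT visit is not, and no study total is given. On neither reading does a stated total cover two CT visits with any repeat.

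**Step 5. Can eligible participants do it?** Section IX asks for a smoking history and does not require current smoking or vaping. An eligible former smoker who does not vape has nothing to bring, and the text gives no alternative.

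**The case against.** The strongest objection is that this is leftover text that nobody would act on. The aims, visit descriptions, Table 1, risks and outcomes all leave the step out, and 640 mrem matches one pair at each of two visits. The pregnancy-test text also refers to MRI, which appears nowhere else in the plan. All of this fits text carried over from another study. That explanation is plausible, but the documents do not confirm it. If it is right, it supports deletion; the paragraph remains an instruction in the current version until it is removed.

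Several narrower objections stand in part:

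- Section XI neither counts scans nor rules out a repeat, so the clash there is an omission. Reading the two-scan total as describing only the first of two sequences is possible, but strained.
- Participants are asked, not compelled, and the wording refers to their own cigarettes or device. For a current user the added exposure is one cigarette or an unspecified amount of vaping. The harm from that is not quantified here, and the point about former smokers is secondary.
- The 640 mrem figure is not in itself evidence of a dose error, because it fits two readings.
- A repeat at baseline only sits poorly with the instruction that the 6-week visit follow the baseline sequence. The 960 mrem case is therefore less natural than 1,280 mrem, although the paragraph's reference to a single unnamed visit leaves it open.
- CT measures are secondary outcomes and are absent from the SAP, so the primary comparison is unaffected.

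These points limit the framing. None supplies a purpose or a risk assessment for the step.

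**Conclusion.** The concern holds. Section XII contradicts itself on the number of scans, and it contains a smoking or vaping step that no aim, outcome, schedule entry, eligibility criterion or risk entry supports. The seriousness comes from participant safety: exposure to smoke or vapour in a vulnerable population, plus 320 to 640 mrem of additional CT dose if 640 mrem is the intended study total. That would take the whole-study dose from 16% to 24% or 32% of the protocol's own reference limit.

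The figures assume 160 mrem per volumetric scan, two CT visits, no scout dose, and the 4,000 mrem limit implied by the protocol's rounded percentages. Nothing in the documents shows whether the step was ever carried out. The consent pages were not available, so nothing is concluded about what participants were told. No outcome bias is claimed: the scans before smoking come first in each session and are the natural source for the CT outcomes, although the protocol does not name them as such.

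**What to change.** Delete the three-sentence paragraph in the CT procedure of Section XII, from the request to bring cigarettes or e-cigarettes through the instruction to rescan. Reword the final dose line to say that 640 mrem is the total for the whole study: 2 volumetric scans × 2 visits × 160 mrem. The reference to MRI in the pregnancy-test text can be removed in the same amendment as housekeeping. The cost is amendment wording only; visits, scheduled procedures, outcomes and sample size do not change.

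If the sponsor does intend the step, the change is larger. The amendment would need to:

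- state the scientific purpose;
- say which participants and which visit or visits it applies to;
- add it to Section XI and Table 1;
- add smoking or vaping exposure and the extra radiation to Section XIII;
- give the correct study dose, 960 mrem for a repeat at one visit or 1,280 mrem for both;
- name the scans taken before smoking as the source for Aim 2.

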Design: We will include COPD subjects with a post-bronchodilator FEV1%predicted below 70% and chronic bronchitis. We will include subjects with at least 2 exacerbations in the last year to identify patients with significant burden due to chronic bronchitis. We will exclude subjects with recent respiratory events or procedures as we want to capture the benefit of HHHFA on chronic, stable COPD participants. Subjects who meet eligibility criteria will be randomized to HHHFA(intervention arm) or usual care (usual care arm). At baseline we will perform measurements in all subjects that include dyspnea, cough, health-related quality of life, and sleep quality questionnaires, spirometry, a 6-minute walk test, and chest CT. The HHHFA device will be provided to participants at the baseline visit.

Protocol: Heated, humidified high-flow air in Chronic Bronchitis

October 8, 2020

HHHFA V4.0

Subjects will use the device during sleep for 6 weeks and return for an end-of-study visit. At the follow-up visit (6 weeks), participants will repeat all baseline evaluations. At the follow-up visit, participants using the HHHFA will be asked whether they want to continue to participate in the sub-study. For participants that have consented to participate in the sub-study, they will use the HHHFA device for an additional 42 weeks. We will follow these participants who continue to use the HHHFA for 42 additional weeks (total 48 weeks) to assess for respiratory exacerbations.

We will compare changes in variables (e.g. FEV1 etc) over time in each treatment group. We will also compare changes in variables over time between groups. To evaluate the effect of treatment, we will use linear mixed effect models controlling for demographics and lung function.

II. Background

COPD is a leading cause of mortality in the U.S.[1] and worldwide[2] and is associated with high morbidity[3] and resource utilization[3], including costs due to clinic visits, chronic therapy, and frequent hospitalizations.[3, 4] COPD patients experience respiratory exacerbations defined as acute worsening of dyspnea, cough, and sputum production.[5]

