- False positive scan, which is an abnormality that initially is of concern that is later found not to be a concern. Anxiety may result from false positive results.
- Detection of abnormalities that could lead to unnecessary testing or treatment.
- Failure to detect an abnormality that is present and possibly miss an opportunity for care.

XIV. Adverse Event Assessment

Adverse event information will be collected from all participants at every encounter throughout the study. The investigator and research team will inquire about adverse events until the end of the study at the 6-week follow up study. Medical records will be reviewed for adverse effects.

XV. Adverse Event Reporting

Adverse events will be evaluated by the investigatory for severity and relatedness. Severe adverse events defined as those that interfere participant's daily activity and/or require treatment will be reported to the manufacturer.

XVI. Data Management

The following people/agencies may have access to subject data/records:

- Study team
- Federal government regulatory agencies
- Auditing departments of the University of Iowa
- University of Iowa IRB
- The National Institute of Health

To protect confidentiality, we will assign each subject a study ID. All records will be in a locked cabinet in a locked office or password protected computer system. Data and records will be managed as follows:

- Paper/hard copy records (hard copy surveys, questionnaires, case report forms, pictures, etc.)
 - Whenever possible, subject identifying information will be blacked out on all paper or hard copy records and replaced with the subject's unique study identifier. Paper records will be stored in a locked file cabinet in the study team's locked office.
- Electronic records (computer files, electronic databases, etc.) – All electronic data bases will only be accessed by the study team and available only with a username and password assigned to study team by the PI.

XVII. Subject Safety

- To minimize risks all subjects are carefully pre-screened and screened trying to identify any factors that could contribute to increased risk.
- All testing is completed at University of Iowa Hospitals and Clinics by a very experienced and well-trained staff and monitored by the Principal Investigator.
- All confidential information is kept in locked offices and password protected computers only available to study team members.
- The participant has contact information and study team members available 24/7.

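### The protocol contradicts itself on whether adverse events are asked about after week 6, while sub-study participants use the device to week 48

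*Protocol*

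**What the plan says.** **End of inquiry.** The second sentence of Protocol Section XIV says that the study team "will inquire about adverse events until the end of the study at the 6-week follow up study".

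**Scope of collection.** The sentence before it reads: "Adverse event information will be collected from all participants at every encounter throughout the study". The sentence after it adds a second source, with no end date: "Medical records will be reviewed for adverse effects".

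**Length of device use.** The Design paragraph of Section I sets out the main study: "Subjects will use the device during sleep for 6 weeks and return for an end-of-study visit". For those who consent to the sub-study, "they will use the HHHFA device for an additional 42 weeks", a total of 48 weeks.

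**Call narratives.** Section XI describes the last sub-study call in these words: "Only participants in the HHHFA sub-study group will receive a phone call at 48 weeks. Assessment for respiratory exacerbations will be performed". The narratives for weeks 12, 24 and 36 have the same content. The week-1 call narrative does name adverse events.

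**Schedule table.** Table 1 in Section XI has seven contact columns (visit 1, week 1, week 6, and the calls at weeks 12, 24, 36 and 48). Its row reads "Adverse events X X X X X X X", so every column is marked.

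The SAP does not mention adverse events.

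**The concern.** Section XIV is where a reader looks for the adverse-event rule, and it gives inquiry an end date that falls 42 weeks before sub-study participants give up the device. The narratives of the four later calls do not contradict that end date, because they mention exacerbations alone. Someone preparing a call form from Sections XI and XIV, without checking Table 1, could leave adverse events out.

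What is at stake is detection of harm during home use at night. Section XIII lists burns, nosebleed, skin injury and low oxygen from improper use among the device risks, and reports adverse effects in 6 of 32 participants in an earlier trial of night-time use. All scheduled sub-study contact after week 6 is by telephone. Milder events, such as skin irritation or a nosebleed, may never reach a medical record, so record review is a weak substitute for asking. Reporting to the manufacturer under Section XV depends on an event first being found. If some calls included the question and others did not, counts of events after week 6 would be hard to interpret.

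**Working it through.** **1. The plan's own total.** Main-study device use is 6 weeks and the sub-study adds 42 (Section I): 6 + 42 = 48 weeks. This agrees with the stated total.

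**2. The two rules side by side.**

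| Source | Inquiry at weeks 12 to 48? |
|---|---|
| Section XIV, first sentence | Yes, if the study includes the sub-study |
| Section XIV, second sentence | No; inquiry ends at week 6 |
| Section XI, four call narratives | Not named; exacerbations only |
| Table 1, adverse-event row | Yes, at all four calls |

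The first sentence of Section XIV does not settle the matter alone. The next sentence places the end of the study at week 6, and Section I also treats the 6-week visit as the end of the study, so the study could be read as the first 6 weeks only. Table 1 cannot be read that way, because it marks the four sub-study columns individually.

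**3. If the second sentence of Section XIV is followed.** Device time after the cut-off is 48 − 6 = 42 weeks, and 42 / 48 = 0.875, or 87.5% of a continuing participant's device time. Scheduled adverse-event inquiries in that period: 0.

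**4. If Table 1 is followed.** Contacts fall at about weeks 0, 1, 6, 12, 24, 36 and 48. The intervals are 1, 5, 6, 12, 12 and 12 weeks. There are 4 inquiries after week 6, the longest interval is 12 weeks, and no part of the 42 weeks lies outside scheduled inquiry.

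**5. Scale across the arm, under step 3 only.** The documents give no continuation rate, so these are assumed cases. At 2:1 randomization of 30 subjects the device arm has 30 × 2/3 = 20, taken here as all completing 6 weeks.

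- All 20 continue: 20 × 42 = 840 of 20 × 48 = 960 device person-weeks fall after the cut-off (87.5%).
- Half continue: 10 × 42 = 420 of 20 × 6 + 420 = 540 (77.8%).
- None continue: 0 of 120.

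Under step 4 each of these counts of uncovered person-weeks is zero.

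**The case against.** The strongest reply is that the intended rule can be recovered. The four later columns of Table 1 exist only for the sub-study, so that row was written with those calls in mind. The first sentence of Section XIV agrees with it. The 6-week sentence can be read as describing the main study alone, since the extension is called a sub-study throughout.

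The silence of the call narratives also proves little. The baseline and 6-week narratives do not name adverse events either, yet Table 1 marks both contacts and Section XIV plainly covers week 6. The later call narratives also omit device training and support, which Table 1 marks at each call. The restriction in those narratives is on who is called, not on what is asked. Outside the calls, record review has no end date, and Section XVII gives participants round-the-clock access to study staff.

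Most of this stands. A reader might infer from Section XIV and the narratives that adverse events go unasked after week 6, or that Section XIV overrides Table 1. The documents support neither: they set no order of precedence, and Section XIV is itself divided. Nor is any 48-week safety summary planned that such a gap would undermine; the stated purpose of the extra 42 weeks is to assess exacerbations.

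What the reply does not remove is the sentence itself. It gives an end date that conflicts with Table 1 for every sub-study participant, and recovering the intention requires the reader to decide that one of two explicit statements does not apply.

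**Conclusion.** The contradiction is real and should be corrected. As written, the end date in the second sentence of Section XIV does not fit a sub-study with device use to week 48, and it conflicts with Table 1.

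The consequence lies between two readings: four scheduled inquiries after week 6, at most 12 weeks apart, or none in 42 of 48 device weeks (87.5%). The second is the worst case and holds only if staff apply the 6-week sentence over Table 1 and over the sentence before it. Even then, record review and participant-initiated contact would remain. It should not be reported as an established absence of safety follow-up.

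The 6, 42 and 48 weeks and the contact schedule come from the protocol. The person-week figures rest in addition on 20 device participants and on assumed continuation rates, and should be taken as illustration only. Confidence is high that the passages conflict; which rule staff would follow cannot be judged from the documents.

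**What to change.** Reword the second sentence of Section XIV so that adverse events are asked about through the 6-week visit for all participants, and through the week-48 call for those in the sub-study. Add adverse events to the Section XI narratives for the calls at weeks 12, 24, 36 and 48. Table 1 needs no change.

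This takes a few words in two sections and adds no visit or procedure. The only downside is a slightly longer call, and Table 1 already schedules that content. If the calls have already begun, record for each one whether adverse events were asked about, so that a call with no event reported can be told apart from a call where the question was not put.
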